#### **6.1.4.5. Follow-up Period**

The follow-up period will begin once a patient has discontinued study treatment. Follow-up period includes disease assessment follow-up (for patients who discontinue study treatment for a reason other than iCPD per iRECIST) and survival follow-up.

Patients who discontinue study treatment without experiencing iCPD will continue to undergo tumor assessment and evaluation of CA-125 (Phase 2), according to the SOA until up to 24 months after last dose of study drug, the start of new anticancer therapy, iCPD per iRECIST, death, loss to follow-up, withdrawal of consent, or the end of the study, whichever occurs first.

Patients who discontinue study treatment when experiencing iCPD per iRECIST with study drug, or patients who discontinue study treatment without experiencing iCPD per iRECIST, but who experience iCPD per iRECIST or start new anticancer therapy during disease follow-up will be assessed for survival and new anticancer treatment status per the SOA, until up to 24 months

after the last dose of study drug, death, withdrawal of consent, loss to follow-up, or end of the study, whichever occurs first.

[figure not shown]
The safety and tolerability of DSP-7888 Dosing Emulsion in combination with immunotherapy PD-1 inhibitors will be assessed for the duration of study treatment and follow-up (see [Table 7](#), [Table 8](#), and [Table 9](#) for the respective SOAs).

All AEs will be collected and recorded for each patient from the date of signing the main ICF for the study until 30 days after last study drug administration. Any pregnancies that occur within 180 days after last study drug administration are to be captured. An AE will be followed until it is either resolved, has returned to baseline, or is determined to be a stable or chronic condition (see [Table 7](#), [Table 8](#), and [Table 9](#)).

[figure not shown]

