Particular attention should be given to the follow up of any **Grade 3 or higher** injection site reactions ongoing at the End of Treatment period until resolution, return to baseline, determined to be a stable or chronic condition or until the patient is lost to follow up or the patient has died. Please record the data within EDC per eCRF instructions. In the instance of resolution with sequelae, please be sure to enter the sequelae as a separate AE (eg skin discoloration, persistent induration, scarring “from ISR”). To facilitate this careful follow up, please consider use of video teleconference with the patient during the follow up period post study.

Objective disease assessments will be performed according to RECIST and iRECIST. For Phase 1b, the first assessment will be performed during Cycle 3, at 4 weeks for the nivolumab arm and at 6 weeks for the pembrolizumab arm, and at Weeks 12, 18, and 24, after the first dose of DSP-7888 Dosing Emulsion. After that, objective disease assessments will occur every 12 weeks until patient discontinuation from the study. For Phase 2, patients will be evaluated for objective response to study drug treatment with radiographic imaging every 6 weeks for 24 weeks and then every 12 weeks until progression.

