5.1. General Statistical Methods

5.1.1. Analysis for Continuous Data

Descriptive statistics, including the mean, standard deviation, median, minimum and maximum values will be provided for continuous endpoints.

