- Onset time of the first Grade 3 or higher ISR for patients with at least one Grade 3 or higher ISR: Time to onset is analyzed for patients with at least one Grade 3 or higher ISR from the first dose of DSP-7888 to the first occurrence of the Grade 3 or higher ISR.
- Onset time of the first Grade 3 or higher ISR: Time to first Grade 3 or higher ISR is defined as the time from the first dose of DSP-7888 to the first occurrence of the Grade 3 or higher ISR. For patients with no Grade 3 or higher ISR, the onset time will be censored as data cutoff date, end of study date, death date, or safety follow-up completion date (end of treatment date + 30 days) whichever is shorter.
- Duration of ISR and Duration of Grade 3 or higher ISR and may be analyzed in the CSR. The duration is defined as (end date – start date + 1), and for ongoing ISR/ or ongoing Grade 3 or higher ISR, the ISR end date is truncated as the minimum of {by data cutoff date, end of study date, death date, last known to be alive date, or safety follow-up completion date (end of treatment date + 30 days)} whichever is shorter.

A listing of ISR will also be provided.

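### If ISR duration is analysed, ongoing reactions are given an end date no later than end of treatment + 30 days without censoring, while resolved ones are uncapped, so duration is understated

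*SAP*

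**What the plan says.** The ISR part of SAP 5.4.1 makes the analysis optional: "Duration of ISR and Duration of Grade 3 or higher ISR and may be analyzed in the CSR". It then gives the formula: "The duration is defined as (end date – start date + 1), and for ongoing ISR/ or ongoing Grade 3 or higher ISR". Where a reaction has no end date yet, a substitute is supplied: "the ISR end date is truncated as the minimum of" five dates. These are data cutoff, end of study, death, last known alive, and EOT + 30 days. The rule covers ISRs of any grade and, separately, Grade 3 or higher.

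The bullets just before it, on time to first ISR, use different language. For the Grade 3 or higher version: "For patients with no Grade 3 or higher ISR, the onset time will be censored as data cutoff date", with a list of alternatives ending "or safety follow-up completion date (end of treatment date + 30 days) whichever is shorter". The duration bullet has no such word and names no time-to-event method. The SAP's general rule in 5.1.1 is: "Descriptive statistics, including the mean, standard deviation, median, minimum and maximum values will be provided for continuous endpoints".

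Protocol 6.1.4.5 does not stop the follow-up of an event at EOT+30. For all adverse events: "An AE will be followed until it is either resolved, has returned to baseline, or is determined to be a stable or chronic condition". It asks for particular attention to reactions of at least Grade 3, and describes these as "injection site reactions ongoing at the End of Treatment period until resolution, return to baseline, determined to be a stable or chronic condition". Loss to follow-up and death also end that follow-up.

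**The concern.** Two clocks feed one summary. A resolved ISR is measured to its real end, however late. An unresolved ISR is measured to an administrative date that cannot be later than EOT+30, even if the site has recorded it as ongoing well after that. The unresolved time is a lower bound on the duration, but with no censoring stated it would enter a mean or median as if it were the duration.

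ISRs are, by the SAP's own account, the main adverse effect of the product, and SAP section 5 turns the final report into a synoptic safety report. Protocol 8.3.2.2 expects more serious ISRs to resolve slowly. How long reactions last is therefore a question a reader of that report may ask, and the error can only run towards shorter durations.

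**Working it through.** The plan states no ISR duration, so there is no figure to reproduce. The check applies the SAP formula to worked cases and then to a simulation. Day 0 is the EOT date, and duration = end - start + 1.

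**Two reactions, both starting at EOT-10**
- Resolved at EOT+90: 90 - (-10) + 1 = 101 days.
- Still ongoing at EOT+200: observed for at least 200 - (-10) + 1 = 211 days. The assigned end is EOT+30, so the recorded duration is 30 - (-10) + 1 = 41 days.
- The unresolved reaction is recorded as 101 - 41 = 60 days shorter than the resolved one.

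**Six reactions, all starting at EOT-10.** Four resolve at EOT+5, +20, +60 and +90; two are still ongoing at EOT+120.
- SAP rule: 16, 31, 71, 101, 41, 41. Mean = 301/6 = 50.2; median = 41 days.
- Censoring the two ongoing reactions at 131 days: the Kaplan-Meier survival estimate is 5/6 after day 16, 4/6 after day 31 and 3/6 after day 71, so the median is 71 days.

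**Direction.** The assigned end date is never later than the true one. Every affected duration is therefore too short, none is too long, and the mean must fall. The median falls or stays where it is.

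**Size, under assumptions that are not in the documents.** Durations are exponential; onset is uniform over the 12 weeks before EOT; sites follow reactions to EOT+30, EOT+90 or EOT+180; ongoing reactions are assigned EOT+30.

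| True median (days) | Follow-up to | Ongoing | SAP-rule median | SAP-rule mean (true mean) | Kaplan-Meier median |
|---|---|---|---|---|---|
| 30 | EOT+30 | 22% | 30 | 34 (44) | 30 |
| 30 | EOT+90 | 5% | 30 | 38 (44) | 31 |
| 30 | EOT+180 | 1% | 31 | 42 (44) | 30 |
| 60 | EOT+30 | 45% | 45 | 48 (87) | 61 |
| 60 | EOT+90 | 22% | 49 | 54 (87) | 60 |
| 60 | EOT+180 | 8% | 55 | 68 (87) | 60 |
| 120 | EOT+30 | 66% | 57 | 59 (174) | not reached |
| 120 | EOT+90 | 47% | 62 | 64 (173) | 119 |
| 120 | EOT+180 | 28% | 73 | 84 (174) | 121 |

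The EOT+30 rows cannot show the reversal, because no resolved reaction then ends after the cut-off. In the other rows, and in matching runs with a true median of 240 days, ongoing reactions were assigned 59 to 71 days on average, against 83 to 142 days for reactions that resolved after EOT+30.

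**A side effect.** SAP 5.4.1 counts a serious, related event as treatment-emergent whenever it occurs. Such an ISR starting at EOT+45 and still ongoing would get 30 - 45 + 1 = -14 days.

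**The case against.** The strongest reply is that little hangs on this. The duration analysis is optional and descriptive, Phase 2 is single-arm, and no decision rule uses ISR duration. ISR by preferred term and maximum grade, and the onset analyses, do not depend on the rule. An ISR listing is planned, and SAP 4.4 leaves incomplete dates unimputed in listings, so ongoing cases should stay visible. All of this stands and limits the importance of the point. A listing does not, however, correct a biased summary.

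It can also be said that the SAP never states that ongoing ISRs count as completed. That is right: it is an inference from an assigned end date, the absence of censoring next to bullets that do censor, and the default descriptive statistics. If censoring was intended, the text still needs to say so.

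A reader might infer four stronger things that the documents do not support.
- *That the worst reactions are the ones shortened.* The rule applies to ongoing ISRs of any grade, and the severity tables are untouched. Protocol 6.1.4.5 also has sequelae such as scarring entered as a separate event when an ISR resolves with sequelae, so some lasting damage leaves the ISR itself with an end date.
- *That unresolved ISRs will in general be recorded as shorter than resolved ones.* With a true median of 60 days, the median recorded duration is 63 days for ongoing and 29 for resolved ISRs with follow-up to EOT+30, and 63 against 43 with follow-up to EOT+90. The reversal is a possibility for individual reactions, not a rule.
- *That a particular bias is to be expected.* No resolution data are given, and with a true median near 30 days the reported median does not move.
- *That the data for the fix are certainly in hand.* In Protocol Table 9 routine adverse event collection ends at the EOT visit, and 6.1.4.5 only asks sites to consider video contact afterwards. A last date recorded as ongoing may not exist for every ISR.

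**Conclusion.** The point holds for the optional ISR duration analysis, if it is carried out as written and summarised under the SAP's default for continuous data. The rule then understates the mean whenever an ISR outlasts its assigned end date, understates the median or leaves it unchanged, and can rank an unresolved reaction below a resolved one. That ranking needs resolution dates after EOT+30, which Protocol 6.1.4.5 makes possible.

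The direction follows from the rule alone. The size does not: it rests on assumed exponential durations and assumed follow-up. It runs from no effect on the median (true value about 30 days) to 45 to 55 days reported for a true 60, and 57 to 73 for a true 120. Even in the 30-day case the mean falls, to between 34 and 42 days against 44. The rule should be corrected before any duration is reported, but no trial decision depends on it.

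**What to change.** In SAP 5.4.1, replace the assigned end date with a censoring rule. Summarise the duration of ISR and of Grade 3 or higher ISR by Kaplan-Meier, censor each ongoing reaction at the last date it was recorded as ongoing, and report the number and percentage unresolved beside the median.

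If no such date is recorded after EOT+30, apply one common cut-off at EOT+30 to resolved and ongoing reactions alike, censor at it, and label the result as duration within that window. Under either option, define the EOT date: Protocol Table 9 places the EOT visit 30 days after the last dose, so EOT+30 could mean 30 or 60 days after the last dose. Also say how an ISR that starts after the cut-off is handled.

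The cost is a short SAP edit, a small amount of standard programming, and possibly a longer reported duration. The committed ISR incidence, grade and onset analyses do not change.

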5.4.2. Clinical Laboratory Evaluations

All samples will be analyzed at a central laboratory and collected per Schedule of Assessments in the protocol. Local laboratories may be used as deemed necessary by the Investigator in order to make treatment related decisions.

The results of laboratory parameters will be graded according to NCI CTCAE v4.03 for below parameters (Table 12). For patients with both baseline and post baseline assessments, a summary of shift from baseline CTCAE grade to maximum postbaseline CTCAE grade will be provided. All records on or after the first dose (scheduled and unscheduled) until 30 days following the last dose of study drug will be considered as post baseline. Additional parameters may be added for the shift tables. Both scheduled and unscheduled laboratory test results will be included in the shift tables.

For the purposes of summarization in both the tables and listings, all laboratory values will be converted to standardized units. If a lab value is reported using a non-numeric qualifier (e.g., less than (<) a certain value, or greater than (>) a certain value), the given numeric value will be used in the summary statistics, ignoring the non-numeric qualifier.

Table 9: CTCAE Lab Grading Parameters.

	↓	↑
HEMATOLOGY	Anemia	
HEMATOLOGY	White blood cell decreased	
HEMATOLOGY	Lymphocyte count decreased	
HEMATOLOGY	Neutrophil count decreased	
HEMATOLOGY	Platelet count decreased	
CHEMISTRY		Alanine aminotransferase increased

CHEMISTRY	Hypoalbuminemia	
CHEMISTRY		Alkaline phosphatase increased
CHEMISTRY		Aspartate aminotransferase increased
CHEMISTRY		Blood bilirubin increased
CHEMISTRY		Blood Urea Nitrogen Increased
CHEMISTRY	Hypocalcemia	Hypercalcemia
CHEMISTRY		Creatinine increased
CHEMISTRY	Hypoglycemia	Hyperglycemia
CHEMISTRY	Hypomagnesemia	Hypermagnesemia
CHEMISTRY	Hypophosphatemia	
CHEMISTRY	Hypokalemia	Hyperkalemia
CHEMISTRY	Hyponatremia	Hypernatremia

Blood Urea Nitrogen Increased is not in CTCAE grading, SDPO will define as grade 1 is 23 – 26 mg/dL, grade 2 is 27-31 mg/dL, grade 3, >31 mg/dL.

Listings of hematology and biochemistry, urinalysis and coagulation will be provided, including the test result, units, normal range, change from baseline, and CTCAE grade if available.

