**Table 9: Schedule of Assessments (Phase 2, Combination of DSP-7888 Dosing Emulsion and Pembrolizumab for Ovarian Cancer)**

Period	Pre-screening	Screening period	Treatment Period (All procedure must be performed PRIOR to injection of study treatment)										Follow-up Period		Notes
			1			2			3	4	5+*	EOT (30 day after last dose)	Disease follow up**	Survival Follow up	
			1	8	15	1	8	15	1	1	1				
			0	1	2	3	4	5	6	9	12				
Scheduling Window (Days)	-	-28 to 1*	0	±2	±2	±2	±2	±2	±3	±3	±7	+7 a	±7	±14	*Procedures in screening should be completed within 28 days from Cycle 1 Day1
Study Drug Administration															
DSP-7888 Dosing Emulsion			X	X	X	X			X	X	X				
Pembrolizumab						X			X	X	X				
Administrative procedure															
HLA screening informed consent	X														
Informed Consent*		X													*Main informed consent and informed consent for future biomarker (optional) for willing participants
Inclusion and Exclusion criteria		X													
Demography and Medical History		X*													*including COVID-19 history and vaccination history
Prior and Concomitant Medications		X	X	X	X	X			X	X	X	X			
Cancer history and Cancer Prior Treatment		X													

Period	Pre-screening	Screening period	Treatment Period (All procedure must be performed PRIOR to injection of study treatment)										Follow-up Period		Notes	
			1			2			3	4	5+*	EOT (30 day after last dose)	Disease follow up**	Survival Follow up		
Treatment Cycle	Day	Week (from 1 st dose)	1	8	15	1	8	15	1	1	1					
Scheduling Window (Days)	-	-28 to 1*	0	±2	±2	±2	±2	±2	±2	±3	±3	±7	+7 a	±7	±14	
New anticancer therapy														X	X	*Every 12 weeks up to 105 weeks and/or on an ad-hoc basis for safety or regulatory purposes, or a prespecified analysis.
Safety assessment																
Physical Examination*		X	X			X				X	X	X	X			*Inspection of prior injection site will be done
Vital Sign and Weight		X*	X	X	X	X				X	X	X	X			*Height will be measured only at screening
12-lead ECG		X								X			X			
ECHO/MUGA		X														
ECOG performance status		X	X	X	X	X				X	X	X	X			
Adverse Events	X*	X**	X	X	X	X				X	X	X	X**			* SAE related to study procedure will be reported to ██████████ Safety **AE must be collected from the date of main ICF to 30 days after last dose

Period	Pre-screening	Screening period	Treatment Period (All procedure must be performed PRIOR to injection of study treatment)										Follow-up Period		Notes	

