#### **12.1.4. Demographic and Baseline Characteristics**

Baseline is defined as the last non-missing measurement taken before receiving the first dose of study drug. All applicable demographic and baseline characteristics will be summarized with descriptive statistics.

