4.2. Baseline Definition

Baseline is defined as the most recent, non-missing value prior to or on the first study drug dose date within 28 days from first dose.

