5.4.3. Electrocardiograms

A 12-lead Electrocardiogram (ECG) with categorical results (normal; abnormal, not clinically significant; abnormal, clinically significant) will be summarized in the shift summary from baseline to worst post baseline. Post baseline includes non-missing records collected (scheduled and unscheduled) after the first dose of study treatment until 30 days following the last dose of study treatment. QT measurements corrected by heart rate will be used for the data analysis and interpretation. QTc interval will be calculated using Fridericia’s correction. The formula is:

$$\text{Fridericia's correction: } QT_cF = QT / RR^{0.33}$$

where unit of QT is milliseconds (msec) and unit of RR is second (sec). The number and percentage of patients in QT and QTcF (QT and QTcF interval: ≤ 450 msec, > 450 - ≤ 480 msec, > 480 - ≤ 500 msec, and > 500 msec) will be summarized at baseline and maximum post baseline. Categories of maximum changes from baseline (≤ 30 msec, > 30 - ≤ 60 msec, > 60 msec) will be summarized as well.

An ECG result listing that including PR interval, RR interval, QT, QTc, QRS duration and Heart Rate will also be provided.

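### Read by date, the SAP's laboratory window makes the Phase 2 Day 1 pre-dose sample both baseline and post-baseline, so the shift table can hide improvement but not worsening (minor)

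*SAP*

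**What the plan says.** **Baseline.** SAP 4.2: "Baseline is defined as the most recent, non-missing value prior to or on the first study drug dose date within 28 days from first dose". The rule works by date and includes the first-dose date. Protocol 12.1.4 is tighter: "Baseline is defined as the last non-missing measurement taken before receiving the first dose of study drug".

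**Laboratory summary.** SAP 5.4.2: "For patients with both baseline and post baseline assessments, a summary of shift from baseline CTCAE grade to maximum postbaseline CTCAE grade will be provided". Its post-baseline window is "All records on or after the first dose (scheduled and unscheduled) until 30 days following the last dose of study drug". Nothing in 5.4.2 takes the record used as baseline out of that window. SAP 4.3.4 does not do so either; it only says that unscheduled as well as scheduled visits enter post-baseline maxima.

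**Parallel sections.** The ECG section (SAP 5.4.3) takes records "after the first dose of study treatment until 30 days following the last dose of study treatment". The vital-signs section (SAP 5.4.4) also starts after the first dose. Only the laboratory section includes the first dose itself.

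**Schedule.** Protocol Table 9 (Phase 2) has haematology and serum chemistry at screening, on Day 1 of Cycles 1 to 4, from Cycle 5 on, and at end of treatment. Its header states: "All procedure must be performed PRIOR to injection of study treatment". Tables 7 and 8 (Phase 1b) schedule neither test on Cycle 1 Day 1; the first on-study sample there is Day 8.

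**The concern.** In Phase 2 the Cycle 1 Day 1 sample is normally the latest value before treatment, so it is the baseline under both the SAP and the protocol. If the laboratory window is applied by calendar date, the same record is also the first post-baseline value. The shift table sets baseline against the maximum post-baseline grade, so the baseline grade becomes a floor for the value it is compared with.

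Two things follow. A patient whose grades after dosing are all below baseline cannot be shown as improved. A patient with no usable sample after dosing still appears to have both assessments, and is tabulated as unchanged instead of being left out.

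This deserves a sentence because SAP section 5 confines the final study report to safety, and the shift table is the laboratory summary that 5.4.2 specifies; the rest of that section's output is listings.

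**Working it through.** The plan gives no figure to reproduce. The check compares the definitions and then follows them through the table.

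**1. Does the overlap arise?**

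| Item | Source | Cycle 1 Day 1 pre-dose sample, Phase 2 |
|---|---|---|
| Baseline | SAP 4.2 | Included (on the first-dose date) |
| Baseline | Protocol 12.1.4 | Included (before the first dose) |
| Post-baseline, laboratory | SAP 5.4.2, by date | Included |
| Post-baseline, laboratory | SAP 5.4.2, by clock time | Excluded |
| Post-baseline, ECG and vital signs | SAP 5.4.3, 5.4.4 | A pre-dose record is excluded |

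The date reading is the natural one. SAP 4.2 and the study-day rule in SAP 4.3.2 both work by date, the SAP has no collection-time rule for laboratory data, and the word *on* adds little unless it refers to the day.

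**2. Effect on the tabulated grade.** Let b be the baseline grade and m the true maximum grade after dosing. With the baseline record in the post-baseline set, the tabulated value is T = max(b, m).

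- m > b: T = m, shown as worse under either rule.
- m = b: T = b, shown as the same under either rule.
- m < b: T = b, shown as the same instead of better.

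Over all 25 pairs with b and m from 0 to 4:

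| | Worse | Same | Better |
|---|---|---|---|
| Post-dose records only | 10 | 5 | 10 |
| Baseline record also counted | 10 | 15 | 0 |

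These are counts of possible grade pairs, not expected proportions of patients. The worse column does not move, because max(b, m) > b only when m > b.

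**3. Scope.** The rule covers all 23 graded directions in the SAP's CTCAE laboratory table (5 haematology + 18 chemistry). It applies to a Phase 2 patient only where the Day 1 value is the baseline. If the Day 1 sample is missing and a screening value is used, there is no overlap.

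**4. Denominator.** Suppose W of N patients worsen and k have no laboratory sample after dosing and within 30 days of the last dose. The tabulated rate is W/N; the intended rate is W/(N − k). The documents give neither W nor k, so these are assumptions. N is taken at both ends of the 20 to 40 in SAP 2.3, with W at 25% of N:

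| N | W | As written | k = 1 | k = 2 | k = 4 |
|---|---|---|---|---|---|
| 40 | 10 | 25.0% | 10/39 = 25.6% | 10/38 = 26.3% | 10/36 = 27.8% |
| 20 | 5 | 25.0% | 5/19 = 26.3% | 5/18 = 27.8% | 5/16 = 31.25% |

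**The case against.** **The text does not compel the date reading.** SAP 5.4.2 refers to the first dose, not its date, whereas SAP 4.2, 4.3.2 and the treatment-emergent rule in 5.4.1 name a date when they mean one. Taken as an event, the first dose comes after a sample that Table 9 requires before injection, and the overlap disappears. This stands as a limit: the overlap is the natural reading, not the only one. It does not remove the need for a fix, since the present wording supports two different tables.

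**Worsening is what a safety reader looks for, and it is untouched.** This stands in full for the count of worsened patients. A reader might infer that pre-treatment abnormalities are being reported as new on-treatment toxicity. They are not: the table shows baseline grade, so these patients fall on the no-change diagonal.

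**A maximum-grade table is not built to show resolution.** This also stands. A reader might infer that any abnormality that resolves on treatment is misreported. A Grade 2 anaemia that later resolves is still correctly tabulated as Grade 2 to Grade 2 if even one post-dose sample is Grade 2. Only patients whose post-dose values are all below the baseline grade are affected, and the listings still show individual results.

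**Stopping early does not by itself leave a patient without post-dose data.** This stands too. Someone who stops before the next scheduled sample on Day 22 still has an end-of-treatment sample scheduled 30 days after the last dose, and unscheduled samples count. Such a patient is affected only if the end-of-treatment sample is missed, or is taken in the +7-day allowance and so beyond the 30-day limit, and no other sample exists. Hence k is probably small, and nothing in the documents gives its value.

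**Conclusion.** The wording should be corrected; severity is minor. On a date reading of SAP 5.4.2, a Phase 2 Cycle 1 Day 1 pre-dose sample is both baseline and post-baseline. Where it is the baseline, patients whose post-dose grades are all lower are shown as unchanged, and patients without a usable post-dose sample are added to the denominator as unchanged. The first effect needs no numerical assumption. The second is a dilution of worsening percentages: roughly 1 to 3 percentage points with N = 40, and up to about 6 with N = 20, under the assumed 25% worsening and 1 to 4 such patients.

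A reader might go further and conclude that the laboratory shift tables are invalid, or that every improvement cell is empty across the study. The documents do not support that. No false worsening is created, no worsened patient is lost, Phase 1b scheduled samples are outside the overlap, and the effect in Phase 2 depends both on the date reading and on the Day 1 value being the baseline. The output is descriptive, and no decision rule in the SAP uses laboratory shifts.

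**What to change.** In SAP 5.4.2:

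- replace *on or after the first dose* with *after the first dose*, matching 5.4.3 and 5.4.4;
- state that the record used as baseline is never counted as post-baseline;
- state that Day 1 samples without a collection time are treated as pre-dose, in line with Table 9.

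It would also be tidy to align SAP 4.2 with Protocol 12.1.4, so that a Day 1 sample known to be post-dose cannot serve as baseline.

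The cost is a phrase and two sentences in the SAP and about a line of derivation code. No data collection or design element changes.
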